11.2 Ethical conduct of the clinical trial

This clinical trial will be conducted in accordance with the ethical principles originating from the Declaration of HELSINKI declaration (1964) and subsequent amendments, the International Conference on Harmonization (ICH), Good Clinical Practice (GCP) and in compliance with local regulatory requirements.

11.3 Subject information sheet / informed consent

All subjects who participate in this trial will have to be fully informed about the clinical trial in accordance with the applicable regulations and GCP guidelines and in accordance with local legal requirements.

The informed consent form approved by an IRB/EC, will be fully explained to the subject during the baseline visit.

Prior to any clinical trial procedures, the subject will sign and date the informed consent form(s) which is written in the local language. A copy of the signed and dated form(s) will be given to the subject. The investigator is responsible for maintaining each subject's consent form(s) in the investigator's site file (ISF) and providing each subject with a copy of the consent form.

As photographs will be taken during the clinical trial, a specific photograph release consent form approved by an IRB/EC will be fully explained to the subject. Subjects willing to be photographed will sign and date the photograph release consent form before any to take any photograph.

11.4 Contractual requirements

A contractual agreement will be signed between the CRO/Sponsor and each Investigator/Institution. This document will contain supplementary information, including financial terms, confidentiality, the clinical trial schedule, third party responsibility, and publication rights.

11.5 Data collection and archiving

11.5.1 Data Collection

The investigator must maintain required records on all clinical trial subjects.

Data for this clinical trial will be recorded in the subject's source documents and in the eCRF, the product dispensation logs, the subject questionnaires and the investigator questionnaire provided by *GALDERMA R&D*.

All data recorded in the documents described above should be recorded completely, promptly, and legibly using black ink.

The appropriate pages will be collected upon clinical trial completion or at any other time specified by CRO CRA/sponsor.

A complete set of copies will remain at the investigational site.

11.5.2 Source documentation

Investigators must keep accurate separate records of all subjects' visits, and all procedures done, being sure to include all pertinent clinical trial related information from which CRF data will be recorded.

A statement should be made on subject's medical notes indicating that the **subject has been enrolled in GALDERMA R&D protocol RD.03.SPR.114384 and has provided dated and signed informed consent.**

All adverse events with the associated concomitant therapies must be thoroughly documented. Results of any diagnostic tests conducted during the clinical trial will be included in the source documentation.

Subject questionnaires completed after the study treatment and at week 12 are considered as source documents and must be kept by the investigator with other study records.

Telephone conversations with the subjects and/or CRO/ *GALDERMA R&D* concerning the clinical trial may be recorded and kept on file.

11.5.3 Archives

All pertinent data, samples, photos, questionnaires, correspondence, original or amended protocol, all reports and all other material relating to the clinical trial will be maintained securely in *GALDERMA R&D* / Investigator/Institution archives for the legally-required duration of archiving.

If the investigator retires, relocates, or for any other reason withdraws from the responsibility of keeping the clinical trial records, custody must be transferred to a person who will accept the responsibility. The sponsor must be notified in writing of the name and address of the new custodian.

11.6 Insurance

A certificate attesting third party coverage of CRO/*GALDERMA R&D* will be provided upon request.

13 ATTACHMENTS

Appendix 1: Subject questionnaire – Treatment day after daylight exposure

This questionnaire aims to collect information on your feelings and opinions regarding the treatments for your actinic keratoses. There is no “right” or “wrong” answer. Your feedback will help us to better understand your needs and expectations, and they will not affect your future care.

Thank you for taking the time to complete this questionnaire.

Instructions:

- This questionnaire is to be completed immediately after the 2 hours of daylight exposure
- Use a black pen to complete the questionnaire and make sure your answer is legible;
- Tick one box only per question unless otherwise indicated; if you need to change your answer, draw a line through the previous answer and then record the new answer;
- Check for completeness of the questionnaire and give it back to the study doctor at the end of the procedure

1. Date of treatment: ____/____ / ____/____
2. Have you received detailed instructions by your doctor on how to use the study treatment?
 Yes No
3. How convenient do you find the study treatment instructions?
 ₁ Very convenient
 ₂ Convenient
 ₃ Inconvenient
 ₄ Highly inconvenient
4. Was Actinica applied to protect from sunburn during daylight exposure? Yes No
↳ Time of sunscreen application (hr/hr : min/min- use 24 hour clock): ____/____ : ____/____
5. Did you use the provided abrasive skin pad to prepare your skin? Yes No
6. Which anatomical area identified by your doctor did you prepare (check one)?
 - a. Scalp
 - b. Forehead
 - c. Right cheek
 - d. Left cheek
 - e. Chin
7. Were the scales and crusts removed on the whole anatomical area? Yes No

8. Did you roughen the surface of the anatomical area with the skin pad? Yes No

[figure not shown]
9. Time of Luxerm® application (hr/hr : min/min- use 24 hour clock): ____/____ : ____/____

10. At what time did you go outside for 2 hours of daylight exposure (hr/hr : min/min- use 24-hour clock): ____/____ : ____/____

11. At what time did you complete the 2 hours of daylight exposure (hr/hr : min/min- use 24 hour clock): ____/____ : ____/____

12. Did you spend time in the shade during the time you had to stay outdoors? Yes No
↳ If yes, how much time? _____ min

13. Please indicate below how was the overall weather during the daylight exposure?

14. What was the overall temperature during the daylight exposure? 1 10-15°C
 2 15-20°C
 3 20-25°C
 4 25-30°C
 5 >30°C

15. Was the Luxerm® cream removed after the 2 hours daylight exposure? Yes No

16. What was the maximal pain you felt during the duration of the daylight exposure? report below

To be completed after the end of the 2 hours Daylight exposure											
No pain at all		Extreme pain									
	0	1	2	3	4	5	6	7	8	9	10

17. How bothered were you by this pain?

- 1 Not bothered at all
- 2 Bothered somewhat
- 3 Bothered a little
- 4 Bothered
- 5 Bothered a great deal

18. How convenient do you find Luxerm® daylight illumination (staying outside)?

- ₁ Very convenient
- ₂ Convenient
- ₃ Inconvenient
- ₄ Highly inconvenient

19. Globally, how satisfied are you with Luxerm® daylight procedure?

- ₁ Very satisfied
- ₂ Satisfied
- ₃ Somewhat satisfied
- ₄ Not satisfied

20. If you are dissatisfied with Luxerm® daylight procedure, what are the reasons (more than one answer may be chosen)?

- ₁ Treatment not effective
- ₁ Side effects of the treatment.
- ₁ Treatment not easy/convenient to use
- ₁ Other. Please specify: _____

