9.1.1.1 Efficacy variable

- Patient Reported Outcomes: subject questionnaire at treatment day after daylight session and at last visit (week 12 or early termination).
- Lesion complete response rate, defined as the percentage of preexisting and treated lesions in the anatomical area at baseline assessed as clear at week 12

- Subject complete response rate defined as the percentage of subjects with all treated lesions clear in the anatomical area at Week 12.
- Subject partially clear defined as the percentage of subjects with at least 75% lesion complete response in the anatomical area at week 12.
- Number of new AK lesions in the anatomical area.
- Subject's skin aspect at week12: mean score on anatomical area at week12.

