9.1.1.2 Safety variables

- Subject's self-assessment of maximal pain after daylight exposure.
- Incidence and severity of adverse events.

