9.1.3 Data presentation and graphics

All continuous data will be summarized using usual statistics: number of values, mean, median, standard deviation, minimum and maximum, and by frequency distribution (n, %) for qualitative data. For ordinal data, both frequency distribution and usual statistics will be presented. All tables will be presented by clinical trial treatment and by visit (when applicable).

Therapies that have been stopped before the baseline visit will be presented as prior therapies. Those reported at screening or starting between screening and baseline visits and still continuing after baseline will be classified as concomitant therapies.

The adverse events will be descriptively summarized (n, %) for the safety population (APT). The adverse events will be descriptively summarized (n, %) by relationship to clinical trial treatments within System Organ Class (SOC) and preferred term (MedDRA). Subjects will be descriptively summarized (n, %) by intensity (i.e. mild, moderate and severe) of adverse events, SOC and preferred terms. Deaths and serious adverse events will be reported as well as withdrawals due to adverse events. A subject will be counted only once per System Organ Class (SOC) and only once per preferred term even if more than one occurrence of an event was reported within a SOC or preferred term. In the summary by categories of intensity, the adverse event with the highest intensity will be used. The subject will be counted only once per SOC (highest intensity whatever the AE within the SOC) and once per preferred term (highest intensity whatever the AE within the preferred term).

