9.1.4 Statistical analyses

The objective of this trial is to evaluate the subject reported outcome with Luxerm® Daylight field procedure after one treatment session. Also the efficacy and safety of Luxerm® in terms of subject complete response rate will be assessed.

No inferential statistics will be performed. All variables will be descriptively summarized on ITT population and on APT population for the safety variables.

Any changes of the statistical analyses decided after the database lock will be justified and documented.

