Appendix 2: Subject questionnaire–Week 12 / early termination

This questionnaire aims to collect information on your feelings and opinions regarding the treatments for your actinic keratosis performed 3 months ago. There is no “right” or “wrong” answer. Your feedback will help us to better understand your needs and expectations, and they will not affect your future care.

Thank you for taking the time to complete this questionnaire.

Instructions:

- This questionnaire is to be completed 3 months after the treatment of Actinic Keratosis you have received.
- Use a black pen to complete the questionnaire and make sure your answer is legible;
- Tick one box only per question unless otherwise indicated; If you need to change your answer, draw a line through the previous answer and then record the new answer;
- Check for completeness of the questionnaire

1. How satisfied are you with the effectiveness of this treatment to clear AKs?
 ₁ Very satisfied
 ₂ Satisfied
 ₃ Somewhat satisfied
 ₄ Not satisfied
2. How much have you been bothered by any side effects of this treatment (skin reactions)
 ₁ Not bothered at all
 ₂ Bothered somewhat
 ₃ Bothered a little
 ₄ Bothered
 ₅ Bothered a great deal
3. How satisfied are you with the skin aspect of the treated area?
 ₁ Very satisfied
 ₂ Satisfied
 ₃ Somewhat satisfied
 ₄ Not satisfied
4. How long after treatment was the duration of social embarrassment due to skin reactions?
----- (days)
5. What was the last treatment you received prior to your treatment with Luxerm® and daylight illumination?
 ₁ None
 ₂ Cryotherapy
 ₃ Efudix, efurix (5% cream)
 ₄ Aldara, Almiq, Aldiq, Soldara, APO-imiquimod, Terry White Chemist
Imiquimod, Chemmart Imiquimod, Imiquad, Apotex-imiquimod, Imiquad, Ixium
 ₅ Solaraze

₆ Picato

₇ Photodynamic Therapy with a red lamp or a blue lamp (PDT)

₈ Photodynamic Therapy with daylight

₉ Peelings

₁₀ Laser

6. How did you find Luxerm® with daylight exposure compared to your last treatment ticked in question 5 (except if it was option 8 “PDT with Daylight”)?

₁ Better

₂ Similar

₃ Worse

₄ Never treated with previous treatment

7. Would you consider using Luxerm® with daylight illumination again if needed in future?

₀ No

₁ Yes

8. Overall, how satisfied are you with this treatment (regarding the procedure, effectiveness, side effects, skin aspect)?

₁ Very satisfied

₂ Satisfied

₃ Somewhat satisfied

₄ Not satisfied

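### The five-point 'bothered' scale in both subject questionnaires is printed out of order, so the mean, SD and possibly the median planned for these two items would not be valid severity summaries.

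*Combined protocol and SAP*

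**What the plan says.** Appendix 1 item 17 asks how bothered the subject was by the pain. Its options start at "1 Not bothered at all", continue with "2 Bothered somewhat" and "3 Bothered a little", and end with bothered (4) and bothered a great deal (5). Appendix 2 item 2, on side effects, prints the same five labels in the same order, with "Bothered somewhat" again in second place.

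Section 9.1.1.1 lists among the analysed variables "Patient Reported Outcomes: subject questionnaire at treatment day after daylight session and at last visit". Section 9.1.3 states: "For ordinal data, both frequency distribution and usual statistics will be presented". The same section defines the usual statistics as the number of values, mean, median, standard deviation, minimum and maximum. It does not name the two items, but a graded 1-to-5 response is most naturally read as ordinal. Nothing in the text available recodes these items or exempts them from numerical summary. Section 9.1 leaves detailed conventions to a separate SAP, to be finalised before database lock.

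**The concern.** A mean or median of category codes describes severity only if the codes rise with severity. Here the end anchors rise, but the step from 2 to 3 goes down in wording, from somewhat to a little. Each label carries its own code and the order is the same in two separate appendices, so this is unlikely to come from reading the PDF.

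The consequence depends on how subjects use the form:

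- **By the words.** The printed codes rank two categories the wrong way round. The mean and SD then misstate how bothered subjects were. The median does too if it falls in either category, as can the minimum and maximum.
- **By position on the list.** The codes rank correctly, but the labels shown against categories 2 and 3 in the tables mislead.
- **A mixture.** Swapping codes 2 and 3 afterwards could not fully repair the data. This is a risk; nothing in the documents shows that it happens.

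Subject-reported outcome is the main objective (section 3.1), and section 3.2 assumes better tolerability in terms of pain. Item 17 is the only question on how bothersome the pain was, since the NRS records only its maximum. Appendix 2 item 2 is the only rating by the subject of bother from side effects.

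**Working it through.** **The plan's own figure.** The only numerical design statement is in section 9.2.2: about 85% satisfaction, 50 subjects, precision 10%. Assuming a 95% Wald interval, the half-width is 1.96 × √(0.85 × 0.15 / 50) = 0.099. The figure reproduces. It concerns overall satisfaction and does not depend on the 'bothered' items.

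**Inputs.** The codes come from Appendix 1 item 17 and Appendix 2 item 2, and n = 50 from section 4.1. The documents give no expected response counts, so all counts below are assumptions chosen to show the range. The correct order is taken to be a little = 2 and somewhat = 3.

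**Formula.** Let pL be the share answering a little and pS the share answering somewhat, with subjects answering by the words. Codes 1, 4 and 5 contribute equally under both orderings, so

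printed mean − ordered mean = (3pL + 2pS) − (2pL + 3pS) = pL − pS.

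**Worked case.** Counts in printed order 15/5/22/6/2:

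- Printed mean: (15 + 10 + 66 + 24 + 10)/50 = 125/50 = 2.50.
- Ordered mean: (15 + 15 + 44 + 24 + 10)/50 = 108/50 = 2.16.
- Difference: (22 − 5)/50 = +0.34.
- SD: 1.165 printed, 1.113 ordered.
- Median: the 25th and 26th values are 3 in the printed codes and 2 in the ordered codes.

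**Range of cases** (counts for not at all / somewhat / a little / bothered / a great deal):

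| Assumed counts | Printed mean | Ordered mean | Difference | Printed median | Ordered median |
|---|---|---|---|---|---|
| 5/5/30/8/2 | 2.94 | 2.44 | +0.50 | 3 | 2 |
| 15/5/22/6/2 | 2.50 | 2.16 | +0.34 | 3 | 2 |
| 15/22/5/6/2 | 2.16 | 2.50 | −0.34 | 2 | 3 |
| 28/4/12/4/2 | 1.96 | 1.80 | +0.16 | 1 | 1 |
| 40/3/4/2/1 | 1.42 | 1.40 | +0.02 | 1 | 1 |
| 15/15/15/4/1 | 2.22 | 2.22 | 0.00 | 2 | 2 |

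The error can go either way. It vanishes when the two middle counts are equal. It is small when most subjects answer not at all. The median is safe when it falls in category 1, 4 or 5.

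**Merged scale.** Combining a little and somewhat gives four levels: 1 not at all, 2 a little or somewhat, 3 bothered, 4 a great deal. The case 15/5/22/6/2 becomes 15/27/6/2, with median 2. The case 40/3/4/2/1 becomes 40/7/2/1, with median 1. Because the two disputed categories share one level, the result is the same whichever order is assumed.

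**The case against.** The strongest objection is that the text subjects actually see is unknown. The trial runs only in Germany, and the forms are probably in German although the protocol does not say so. The German labels may rise correctly, and the separate SAP may recode the items. This stands as a limit: the error is demonstrated for the English text and its codes, and its effect on the data is conditional. It does not remove the need to compare the German form and the eCRF codes with the protocol.

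A second objection is that the labels are undefined and close in meaning, and that in the satisfaction items somewhat marks the weakest positive step, next to not satisfied. That makes somewhat in second place less strange. It does not explain why a little is coded above it.

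A third is that little depends on these items. They are 2 of 29 questionnaire items (20 + 9), and section 9.1.4 says "No inferential statistics will be performed". Section 9.1.3 also requires frequencies, which are correct by label if subjects answer by label. Section 9.1.1.2 lists separately the "self-assessment of maximal pain after daylight exposure", rated 0 to 10. All of this is true and limits the reach. It does not make the planned mean and SD of the misordered codes meaningful.

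Finally, section 2.1 describes the treatment as almost painless. For item 17 the case with a shift of 0.02 may therefore be nearer the truth than the one with 0.34. That is plausible, but the documents give no expected counts for either item, and skin reactions could produce more answers in the middle.

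**Conclusion.** The concern holds. As printed in English, both 'bothered' items are misordered at codes 2 and 3, and the plan as written would produce numerical summaries from those codes. If subjects answer by the words, the mean is wrong by the share answering a little minus the share answering somewhat. In the assumed examples this runs from zero to about a third of a point, and to half a point in the most unequal case, in either direction. The median can move by one category.

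This rests on three assumptions: the ordinary English ranking of the two adverbs, the treatment of these items as ordinal under section 9.1.3, and no recoding in the separate SAP. Confidence is high for the misordering in the English text and moderate for its effect on the data, because the German wording is not available. The satisfaction items, the pain NRS, adverse event severity and the 10% precision statement are not affected. It should be corrected, but it does not threaten the trial's main descriptive results.

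**What to change.** Check the administered German wording and the eCRF code list for both items first.

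- **Forms not yet in use.** Reorder both items to 1 not bothered at all, 2 bothered a little, 3 bothered somewhat, 4 bothered, 5 bothered a great deal, and make the German version and the eCRF codes match. The cost is two option lists, one code list and one translation check.
- **Forms in the printed order already in use.** State in the SAP, before database lock, that these two items are reported as frequencies by label, with a little and somewhat also shown merged, and that no mean or SD of the printed codes is given. A median category on the merged four-level scale is acceptable. The cost is one sentence.

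If the German form already rises correctly and the eCRF codes follow it, only the English appendices need correcting and the planned summaries can stand.

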Appendix 2: Subject questionnaire–Week 12 / early termination

This questionnaire aims to collect information on your feelings and opinions regarding the treatments for your actinic keratosis performed 3 months ago. There is no “right” or “wrong” answer. Your feedback will help us to better understand your needs and expectations, and they will not affect your future care.

Thank you for taking the time to complete this questionnaire.

Instructions:

- This questionnaire is to be completed 3 months after the treatment of Actinic Keratosis you have received.
- Use a black pen to complete the questionnaire and make sure your answer is legible;
- Tick one box only per question unless otherwise indicated; If you need to change your answer, draw a line through the previous answer and then record the new answer;
- Check for completeness of the questionnaire

1. How satisfied are you with the effectiveness of this treatment to clear AKs?
 ₁ Very satisfied
 ₂ Satisfied
 ₃ Somewhat satisfied
 ₄ Not satisfied
2. How much have you been bothered by any side effects of this treatment (skin reactions)
 ₁ Not bothered at all
 ₂ Bothered somewhat
 ₃ Bothered a little
 ₄ Bothered
 ₅ Bothered a great deal
3. How satisfied are you with the skin aspect of the treated area?
 ₁ Very satisfied
 ₂ Satisfied
 ₃ Somewhat satisfied
 ₄ Not satisfied
4. How long after treatment was the duration of social embarrassment due to skin reactions?
----- (days)
5. What was the last treatment you received prior to your treatment with Luxerm® and daylight illumination?
 ₁ None
 ₂ Cryotherapy
 ₃ Efudix, efurix (5% cream)
 ₄ Aldara, Almiq, Aldiq, Soldara, APO-imiquimod, Terry White Chemist
Imiquimod, Chemmart Imiquimod, Imiquad, Apotex-imiquimod, Imiquad, Ixium
 ₅ Solaraze

₆ Picato

₇ Photodynamic Therapy with a red lamp or a blue lamp (PDT)

₈ Photodynamic Therapy with daylight

₉ Peelings

₁₀ Laser

6. How did you find Luxerm® with daylight exposure compared to your last treatment ticked in question 5 (except if it was option 8 “PDT with Daylight”)?

₁ Better

₂ Similar

₃ Worse

₄ Never treated with previous treatment

7. Would you consider using Luxerm® with daylight illumination again if needed in future?

₀ No

₁ Yes

8. Overall, how satisfied are you with this treatment (regarding the procedure, effectiveness, side effects, skin aspect)?

₁ Very satisfied

₂ Satisfied

₃ Somewhat satisfied

₄ Not satisfied

9. If you are dissatisfied with Luxerm® daylight procedure, what are the reasons (more than one answer may be chosen)?

₁ Treatment not effective

₁ Side effects of the treatment

₁ Luxerm® daylight procedure not easy/convenient to use

₁ Skin aspect of the treated area

₁ Other. Please specify: _____

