4.2.2 Exclusion criteria

Any subject who meets one or more of the following exclusion criteria will not be included in this clinical trial.

1. Subject with a clinical diagnosis of a skin disease other than AK (including non-melanoma skin cancer) on the target anatomical area.
2. Subject with severe AK (thick, hyperkeratotic AK) per anatomical area (face or scalp).

3. Subject with clinical diagnosis of other skin disease on the target anatomical area.
4. Subject with pigmented AK on the target anatomical area.
5. Subject with melanoma at any location.
6. Immunocompromised subject or requiring immunosuppressive therapies.
7. Subject with porphyria; photosensitivity- related disorders, active infectious disease.
8. Subject with known or suspected hypersensitivity to the active substance or to any excipients of Luxerm® (see Summary of Product Characteristics).
9. Female subject who is pregnant, nursing or planning a pregnancy during the study.
10. Subject who has used any of the following topical preparations on the area to be treated: keratolytics including urea (greater than 5%), alpha hydroxyacids [e.g. glycolic acid, lactic acid, etc. greater than 5%], salicylic acid (greater than 2%) within 2 days of initiation of treatment.
11. Subject with a wash-out period from baseline for topical or systemic treatment or medical/surgical procedure in the anatomical area (for AKs) less than the following:

• Retinoids, including tazarotene, adapalene, tretinoin, retinol	4 weeks
• Cryotherapy, diclofenac, corticosteroids or other treatments for AK	8 weeks
• Microdermabrasion, laser ablative treatments or chemical peels	8 weeks
• 5-FU, imiquimod	24 weeks
• Surgical: excision and reconstructive surgery, chemosurgery,	12 weeks
• Any Photodynamic Therapy, ingenol mebutate (Pep-005), Radiotherapy and UV radiation therapy	12 weeks
• Investigational therapies for Actinic Keratoses	12 weeks
• Immunosuppressive drugs (such as glucocorticoids, cytostatic, antibodies, drugs acting on interferon, opioids, TNF binding proteins, Mycophenolate, small biologics agents)	12 weeks
12. Subject who is currently participating to/ or who has participated in another investigational treatment or device research study within 4 weeks of baseline visit.
13. Subject may be unreliable for the study including subjects who engage in excessive alcohol intake or drug abuse, or subjects who are unable to return for scheduled follow-up visits.

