5.5.3 Week 12 / Last clinical trial visit or Early trial termination visit

1. Question the Subject about AEs by asking an open-ended question taking care not to influence the Subject's answer, such as "Have you noticed any change in your health since the last visit, including any potential skin reaction in the treated anatomical area?". Record all events (including Local Skin Reaction), as appropriate on the corresponding CRF pages.
2. Enquire whether any concomitant therapies have been added, stopped, or changed since the subject's last visit. Document all changes in the CRF.
3. Using the transparent sheet which was completed at Baseline, relocate the anatomical area defined at baseline and each treated AK lesion. Assess the lesion response for each treated AK mapped at Baseline (see Sections 7.2.1 and 7.2.1.2). Identify new lesions.

Note: Any lesion in the anatomical area identified at Week 12 but not at Baseline is defined as a new lesion. Total number of new lesions should be recorded in the eCRF.

4. On each AK lesion that has completely responded, perform Investigator Clinical Assessment of the subject's Skin Aspect (see [7.2.2](#)).
5. Assess the skin photodamage of the selected anatomical area using the Dover's modified global photodamage score (see [7.4.1](#)).
6. Conduct a pregnancy test on any female of childbearing potential. In case of positive result, please refer to Section [8.3](#).
7. *For selected sites only*, take photographs of anatomical area according to the provided procedure only if subject has agreed on the approved Photo release consent form.
8. Ask the subject to fill out the subject week 12 questionnaire and collect it. Ensure it is fully completed and with SIN number. Report the week 12 questionnaire in the eCRF.
9. Complete CRF Exit form and discharge Subject from the study.
10. Physician questionnaire should be completed once all subjects from the site have completed the study

At a minimum, the tasks numbered 3, 4, 5, and 9 have to be performed by a Dermatologist.

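### Week 12 question 5 has no true answer for prior surgery, radiotherapy or any other unlisted treatment, and the comparison in question 6 rests on that answer

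*Combined protocol and SAP*

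**What the plan says.** Appendix 2, question 5 asks: "What was the last treatment you received prior to your treatment with Luxerm® and daylight illumination". The options are none, cryotherapy, four topical products or product groups listed by brand, lamp PDT, daylight PDT, peelings and laser. The form's general instruction is "Tick one box only per question unless otherwise indicated", and question 5 gives no exception.

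Question 6 asks: "How did you find Luxerm® with daylight exposure compared to your last treatment ticked in question 5". Its stem goes on to exempt subjects who ticked option 8, daylight PDT. Its answers are better, similar, worse, or, as code 4, "Never treated with previous treatment".

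Section 4.2.2, exclusion 11, lists a 12-week wash-out in the treated area for "Surgical: excision and reconstructive surgery, chemosurgery", and the same interval for radiotherapy and for investigational AK therapies. Section 4.3.1 counts as previous therapies only those stopped within 12 weeks before product application. At week 12, section 5.5.3 tells the site, of the questionnaire: "Ensure it is fully completed and with SIN number".

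Section 9.1.1.1 lists the subject questionnaire as an analysed variable, and section 9.1.4 says that everything is summarised descriptively. The missing-value rule in section 9.1.2.3 deals with lesion response only.

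**The concern.** Subject-reported outcome is the main objective (synopsis and section 3.1), and question 6 is the one place where subjects set Luxerm® against something else. The answer can be read only if the comparator in question 5 is right. For a subject whose last treatment is not on the list, no truthful tick exists. The result is a false comparator, a false report of no prior treatment, or a blank.

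A smaller weakness sits in question 6. Subjects who last had daylight PDT are told not to compare, but there is no box that says so, while both the form and the site instructions press for completeness. Section 9 also does not say which subjects form the denominator of the comparison. What is at stake is the accuracy of one descriptive table.

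**Working it through.** **1. The plan's own figure.** Section 9.2.2 gives a precision of 10% for 85% satisfaction in 50 subjects. With a 95% level assumed (none is stated), 1.96 × √(0.85 × 0.15 / 50) = 1.96 × 0.0505 = 0.099. The figure is reproduced. It concerns overall satisfaction and does not depend on questions 5 and 6.

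**2. Admissible prior treatments against the options in question 5.**

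| Prior treatment in the area | Wash-out (exclusion 11) | Box in question 5 |
|---|---|---|
| Cryotherapy, diclofenac | 8 weeks | yes |
| Laser, peels | 8 weeks | yes |
| 5-FU, imiquimod | 24 weeks | yes |
| PDT, ingenol mebutate | 12 weeks | yes |
| Surgery | 12 weeks | **no** |
| Radiotherapy | 12 weeks | **no** |
| Investigational AK therapy | 12 weeks | **no** |
| Other AK treatments | 8 weeks | **no** |

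Section 2.1 itself counts excisional surgery among the AK treatments. A free-text *Other* is offered in four other items (Appendix 1 question 20, Appendix 2 question 9, Appendix 3 questions 2 and 7), so its absence here looks like an oversight.

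**3. Can the CRF supply the true answer?** Let S be the date on which the earlier treatment stopped, B baseline and T application of Luxerm®.

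- Eligibility for the 12-week items requires S ≤ B − 12 weeks.
- Recording as a previous therapy requires S ≥ T − 12 weeks.
- Treatment follows baseline, normally by up to 1 week with up to 7 further days (sections 4.4 and 5.1), so T ≥ B and T − 12 weeks ≥ B − 12 weeks.

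Both conditions hold only if T = B and S lies exactly 12 weeks earlier. Surgery, radiotherapy and investigational therapy in the treated area therefore normally fall outside the recording window. The general question on relevant medical history at baseline (section 5.5.1) might catch some. The catch-all for other AK treatments differs: with an 8-week wash-out, one stopped between 8 and 12 weeks before application would be recorded.

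**4. What reaches question 6.** A subject whose last treatment was surgery has three routes:

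- tick *None*, then probably code 4 in question 6, and drop out of the comparison;
- tick an older listed treatment and compare with that one, which was not the last;
- leave question 5 blank and answer question 6 with an unrecorded comparator.

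**5. Code 4.** Section 9.1.3 gives ordinal data both frequencies and the usual statistics. If question 6 is handled as ordinal (the plan does not say), each never-treated answer enters as 4 in a mean whose meaningful range is 1 to 3.

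**6. Weight of one answer.** One of 50 is 1/50 = 2 percentage points. The documents do not give the share of subjects without a valid comparison, so the shares below are assumptions. The half-width is 1.96 × √(0.25 / n), the widest case.

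| Assumed share without a valid comparison | Usable n | One answer (1/n) | 95% half-width at 50% |
|---|---|---|---|
| 0% | 50 | 2.0 points | 13.9 points |
| 10% | 45 | 2.2 points | 14.6 points |
| 20% | 40 | 2.5 points | 15.5 points |
| 30% | 35 | 2.9 points | 16.6 points |

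These shares include never-treated and prior daylight-PDT subjects, who are properly out of the comparison. The table shows how much one misfiled answer weighs. It does not estimate how many there are.

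**The case against.** The best defence is that little depends on this. The plan names no breakdown by prior treatment and no better-than-last-treatment rate. A wrong tick in question 5 need not change a subject's view in question 6. Section 9.1 leaves data conventions to a separate SAP that is not part of the combined document, so a denominator rule may be set there. Exclusion 11 is a wash-out list that also covers items such as immunosuppressive drugs; it does not predict what subjects will have had. Of the AK treatments named in section 2.1, only excisional surgery lacks a box. All of this stands and limits the importance of the point. It does not give those subjects a true answer.

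Two stronger readings are tempting and fail:

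- A reader might infer that prior daylight-PDT subjects are forced into error, or that their blanks cannot be told from missing answers. The stem exempts them, so a blank is the intended response. Option 8 in question 5 with question 6 blank is a permitted skip; another treatment ticked in question 5 with question 6 blank is missing. Only the risk of a false tick prompted by the completeness check remains, and option 8 identifies that too.
- A reader might also infer that the items beginning "If you are dissatisfied with Luxerm® daylight procedure, what are the reasons" match no point on the satisfaction scale. The physician form in Appendix 3 uses the same scale and reasons item and routes the lowest category to it, sending the category above to the comments instead. The intended meaning is therefore clear.

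**Conclusion.** The point holds for question 5 and, through it, for question 6. Eligible subjects whose last treatment was surgery, radiotherapy, an investigational AK therapy or another unlisted treatment have no true option. For the 12-week items in the treated area, the CRF therapy pages would not normally correct the answer.

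The size is small. It concerns one descriptive comparison, with each affected subject worth 2 points of 50 and somewhat more once the denominator is restricted. How many are affected cannot be derived from the documents. The conclusion assumes only that some enrolled subjects had such a treatment last, which the eligibility criteria allow.

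A reader might go further and infer that the main satisfaction result is compromised. The documents do not support that: overall satisfaction (Appendix 1 question 19, Appendix 2 question 8), the efficacy endpoints and the precision statement do not use questions 5 or 6. This is a low-priority correction, worth making because it costs little.

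**What to change.** - **Question 5:** add *Surgery/excision* and *Other, please specify*.
- **Question 6:** add *Not applicable (last treatment was daylight PDT)*, so that the completeness check does not prompt a false tick.
- **Analysis:** state in the SAP that better, similar and worse are summarised only among subjects with a non-daylight prior treatment in question 5. Report code 4 and the not-applicable answers as separate counts, outside any ordinal summary.
- **If the forms are already in use:** leave them and apply the denominator rule with question 5 as the filter. Section 9.1 has the SAP finalised before database lock, so there is room for it. Answers already given under the old list cannot be reclassified this way, and the report should say so.

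The cost is the re-issue of one sponsor form, three added eCRF options and a slight loss of comparability with any earlier use of the questionnaire.
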